3.2. Subject Exclusion Criteria

A subject who meets any of the following criteria will be excluded from the study:

1. Chronic pruritus due to a defined primary dermatologic disorder (e.g., atopic dermatitis, psoriasis, etc.).
2. Patients with a prior diagnosis of excoriation disorder.
3. Use of topical treatments for CIP (other than bland emollients) within 1 week of baseline.
4. Subjects receiving systemic immunosuppressive or immunomodulating drugs (eg, oral or injectable corticosteroids, methotrexate, cyclosporine, mycophenolate mofetil, azathioprine) within 4 weeks of Baseline.
5. Subjects with cytopenias at screening, defined as:
 - a. Leukocytes $< 3 \times 10^9/L$
 - b. Neutrophils $<$ lower limit of normal
 - c. Lymphocytes $< 0.5 \times 10^9/L$
 - d. Hemoglobin < 10 g/dL
 - e. Platelets $< 100 \times 10^9/L$
6. Unwilling or unable to follow medication restrictions or unwilling or unable to sufficiently washout from use of restricted medication or under treatment for skin disease with therapy listed in prohibited medications that may influence results of this study.
7. Use of any prohibited medications (see Section 5.6.3) within 14 days or 5 half-lives (whichever is longer) of the Baseline visit.
8. Current clinically significant cardiovascular, respiratory, neurologic, hepatic, hematopoietic, renal gastrointestinal, endocrine or metabolic dysfunction unless currently controlled and stable, including (but not limited to) the following:
 - a. Positive for hepatitis C antibody test (anti-HCF);
 - b. Positive for hepatitis B surface antigen (HBsAg) or hepatitis B core antibody (HBcAb);
 - c. Positive for HIV (DUO test, p24 antigen)

9. Active malignancy.
10. History (including family history) or current evidence of congenital long QT syndrome or known acquired QT prolongation.
11. Exposure to any investigational medication, including placebo, within 60 days of the Baseline Visit.
12. History of intolerance and/or hypersensitivity to medications similar to apremilast.
13. Subjects with prior treatment with apremilast.
14. Subjects with severely impaired liver function (Child-Pugh Class C) or end-stage renal disease on dialysis or at least 1 of the following:
 - a. Serum creatinine > 1.5 mg/dL;
 - b. Alanine aminotransferase or aspartate aminotransferase $\geq 1.5 \times$ upper limit of normal
15. Anyone affiliated with the site or sponsor and/or anyone who may consent under duress.
16. Any other sound medical reason as determined by the Investigator including any condition which may lead to an unfavorable risk-benefit of study participation, may interfere with study compliance or may confound study results.
17. Women who were pregnant or breastfeeding within 4 months before screening.
18. Anyone with prior history of suicide attempt at any time in subject's life prior to screening or randomization or any psychiatric illness requiring hospitalization within last three years.
19. Clinically significant or uncontrolled cardiac disease, including unstable angina, acute myocardial infarction within 6 months from Day 1 of study drug administration, New York Heart Association Class III or IV congestive heart failure, and arrhythmia requiring therapy or uncontrolled hypertension (blood pressure > 150/90 mmHg) unless approved by medical monitor/sponsor.
20. History of alcoholism or drug addiction within 1 year before screening, or current alcohol or drug use that, in the opinion of the investigator, will interfere with the subject's ability to comply with the administration schedule and study assessments.
21. Subjects who anticipate receiving a live or live-attenuated vaccination from screening through the final follow-up visit.
22. Subjects who, in the opinion of the investigator, are unable or unlikely to comply with the administration schedule and study evaluations.

23. Other than disease under study, any clinically significant, as determined by Investigator, cardiac, endocrinologic, pulmonary, neurologic, psychiatric, hepatic, renal, hematologic, immunologic disease or other major disease that is currently uncontrolled.

4. INVESTIGATIONAL PLAN

4.1. Overall Study Design

This study is an open label pilot study examining the efficacy of apremilast in the treatment of CIP. Ten (10) subjects who meet the eligibility criteria are planned to be enrolled. The total duration of subject participation will be 6 study visits over approximately 16 weeks. All subjects will receive apremilast 30 mg by mouth BID for 16 weeks.

All apremilast subjects will have visits at Screening, Baseline, and Weeks 2, 4, 8, 12, 16, and 18 (follow-up). Adverse events (AEs), medication history, clinical assessments, physical exam, and vital signs will be performed at each visit. Clinical safety laboratories will be performed at screening and Week 16 (EOT). All laboratory assessments will be performed using The Barnes-Jewish Hospital laboratory except for urine pregnancy tests (as applicable). NRS and DLQI scoring will be performed by a research nurse.

Two skin biopsies will be performed at the most pruritic site at Baseline and at Week 16 (adjacent to the initial biopsy site) for histopathological analysis and RNA-seq transcriptional analysis.

After the end-of-treatment visit (Week 16, or early termination), subjects will have follow-up assessments two weeks later (week 18) to monitor for durability of effect (relapse rate), AEs, medication history, vital signs, and clinical assessments.

4.2. Measures Taken to Avoid Bias

This is an unblinded open label pilot study so the study will be biased for both the subject and the investigator.

4.3. Number of Subjects

The study will include 10 subjects. Discontinued or drop-out subjects will not be replaced.

4.4. Duration of Treatment and Subject Participation

After signing the ICF, screening assessments may be completed over a period of up to 28 days. Scheduled study visits are at Week 2, 4, 8, 12, and 16. Follow up is at Week 18.

Study participation is expected to be approximately 18-22 weeks per individual subject with variance related to screening process duration.

4.5. Overall Study Duration

The study begins when the first subject signs the informed consent form. The end of the study will occur when all subjects have discontinued study drug and have completed applicable follow-up assessments.

4.6. Study Termination

The investigator retains the right to terminate study participation at any time, according to the terms specified in the study contract. The investigator is to notify the institutional review board (IRB)/independent ethics committee (IEC) in writing of the study's completion or early termination, send a copy of the notification to the sponsor and retain 1 copy for the site study regulatory file.

5. TREATMENT

5.1. Treatment Assignment

5.1.1. Subject Numbering and Treatment Assignment

All subjects will be numbered and coded by the study team.

5.1.2. Randomization and Blinding

There will be no randomization nor blinding in this study.

5.2. Apremilast Tablet

5.2.1. Description and Administration

Apremilast 10 mg tablets will be administered at a dose of 30 mg BID. Instructions will be provided with the study medication. The starting dose is 10 mg daily with titration upwards by 10 mg each day until maintenance dose of apremilast 30 mg BID is reached. The titration schedule is as follows:

Day 1: Apremilast 10 mg in am

Day 2: Apremilast 10 mg BID

Day 3: Apremilast 10 mg in am and Apremilast 20 mg in pm

Day 4: Apremilast 20 mg BID

Day 5: Apremilast 20 mg in am and Apremilast 30 mg in pm

Day 6 and continuing as maintenance: Apremilast 30 mg BID

5.2.2. Supply, Packaging, and Labeling

Apremilast drug product will be provided as Apremilast 10 mg tablets for the titration period. On Day 6, patients will change to 30 mg tablets. All investigational product

labels will be in the local language and will comply with the legal requirements of each country

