
Positive for hepatitis B surface antigen (HBsAg) or hepatitis B core antibody (HBcAb) Positive for HIV (DUO test, p24 antigen)
 
 • Active malignancy • Active substance abuse or history of substance abuse within 6 months of screening • History (including family history) or current evidence of congenital long QT syndrome or known acquired QT prolongation • Exposure to any investigational medication, including placebo, within 60 days of the Baseline Visit • Subjects who had previously received apremilast • Subjects with severely impaired liver function (Child-Pugh Class C) or end-stage renal disease on dialysis or at least 1 of the following: 
 – Serum creatinine > 1.5 mg/dL – Alanine aminotransferase or aspartate aminotransferase $\geq 1.5 \times$ upper limit of normal • Anyone affiliated with the site or sponsor and/or anyone who may consent under duress • Any other sound medical reason as determined by the Investigator including any condition which may lead to an unfavorable risk-benefit of study participation, may interfere with study compliance or may confound study results

Apremilast tablet/Study Drug, Dosage, and Mode of Administration: Study drug will be supplied as apremilast 10 mg tablets and given orally in the following manner. Initial: 10 mg in the morning. Titrate upward by additional 10 mg per day on days 2 to 5 as follows: Day 2: 10 mg twice daily; Day 3: 10 mg in the morning and 20 mg in the evening; Day 4: 20 mg twice daily; Day 5: 20 mg in the morning and 30 mg in the evening. Maintenance dose: 30 mg twice daily starting on day 6.

Reference Therapy, Dosage, and Mode of Administration: As currently prescribed and indicated for psoriatic arthritis and plaque psoriasis.

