5.4.2. Criteria and Procedures for Dose Interruptions and Adjustments of Study Drug

In some circumstances, it may be necessary to temporarily interrupt treatment as a result of AEs or laboratory abnormalities that may have an unclear relationship to study drug. Decisions on dose interruptions or adjustments will be made by the investigator. Should the subject experience a mild AE or laboratory abnormality, the dose will be reduced to 20 mg BID.

Individual subjects may have administration interrupted at the discretion of the investigator for AEs or laboratory abnormalities until these have resolved. Subjects will have administration interrupted in the following situations.

- The subject develops a Grade 2 increase in ALT ($> 3 \times \text{ULN}$) or AST ($> 3 \times \text{ULN}$), or a Grade 2 decrease in ANC ($< 1.5 \times 10^9/\text{L}$) or platelets ($< 75 \times 10^9/\text{L}$), or a Grade 3 decrease in absolute lymphocyte count ($< 0.5 \times 10^9/\text{L}$). Laboratory abnormalities should be confirmed with repeat testing within 48 hours whenever possible and STAT delivery of the laboratory results requested.
- The subject develops a Grade 3 or higher laboratory abnormality, with the exceptions of lipase (in which case a Grade 4, $> 5 \times \text{ULN}$, results in discontinuation of study medication) or any asymptomatic triglyceride, cholesterol, or amylase elevations. Laboratory abnormalities should be

confirmed with repeat testing within a medically indicated timeframe, based upon the investigator's judgment and in collaboration with the sponsor's medical monitor, and STAT delivery of the laboratory results requested.

- The subject had a severe drug-related AE as determined by the investigator.

5.4.3. **Criteria for Permanent Discontinuation of Study Drug**

Subjects who have administration interrupted based on the above criteria will be followed until the parameters return to the normal range or to baseline values. Laboratory evaluations can be repeated as frequently as daily. A subject who has had their dose interrupted based on these criteria may resume administration with study drug at a later time if the subject no longer meets the criteria for interrupting the dose with the sponsor's approval in consultation with the investigator. Subjects who meet withdrawal criteria (see Section 5.5) during study drug interruption will be withdrawn from the study and may not resume administration.

5.5. **Withdrawal of Subjects From Study Treatment**

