6.3. Treatment

Subjects who meet all the study entry criteria and none of the exclusion criteria will return to the study site on Day 1 of administration. Dates for subsequent study visits will be determined based on this day and should occur within the visit windows outlined in the schedules of assessments.

The treatment period begins when the subject receives their first dose of study drug, which will be administered in the clinic. A one month supply will be dispensed to subjects with detailed instructions.

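### The protocol contradicts itself on tablet strength and on dose reduction, and under one pairing of its statements the 20 mg BID dose cannot be made from the tablets supplied

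*Combined protocol and SAP*

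**What the plan says.** On tablet strength there are two accounts.

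- Section 5.2.2: "Apremilast drug product will be provided as Apremilast 10 mg tablets for the titration period", followed by "On Day 6, patients will change to 30 mg tablets".
- Synopsis, study drug paragraph: "Study drug will be supplied as apremilast 10 mg tablets and given orally in the following manner". That paragraph goes on to cover both titration and maintenance. Section 5.2.1 agrees with it: "Apremilast 10 mg tablets will be administered at a dose of 30 mg BID". Its schedule ends with "Day 6 and continuing as maintenance: Apremilast 30 mg BID".

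On dose reduction there are also two accounts.

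- Section 5.4.1 says the trial contains no dose modifications.
- Section 5.4.2: "Should the subject experience a mild AE or laboratory abnormality, the dose will be reduced to 20 mg BID". The sentence just before it reads "Decisions on dose interruptions or adjustments will be made by the investigator".

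On dispensing, section 6.3 says "A one month supply will be dispensed to subjects with detailed instructions" and names no strength. Table 1 schedules dispensing and bottle collection at Baseline and at Weeks 2, 4, 8, 12 and 16. Section 5.3 measures compliance by counting leftover tablets against the expected regimen, with 80% as the threshold.

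**The concern.** Section 5.2.2 is the supply section and the only place that says tablet strength changes on Day 6. Read with section 5.4.2, it puts a subject on 30 mg tablets and then calls for a dose that those tablets cannot make. The site would have to improvise, and the dose actually taken could differ from the dose ordered.

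Two things are at stake. The first is dosing safety: staff working from different sections could hand out different tablets for the same instruction. The second is interpretation. With ten subjects, no replacement (section 4.3) and a within-subject comparison, it matters what each subject was taking when the itch score and adverse events were recorded. The compliance measure is a tablet count, so it has no fixed meaning until strength and regimen are settled.

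**Working it through.** The plan gives no figure of its own to reproduce here. The check is tablet arithmetic and a comparison of sections.

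**1. Titration (synopsis and section 5.2.1).** Daily totals on Days 1 to 5 are 10, 20, 30, 40 and 50 mg, which is 150 mg or 1 + 2 + 3 + 4 + 5 = 15 tablets of 10 mg. From Day 6 the total is 30 + 30 = 60 mg a day. The two schedules agree; only the tablet strength after Day 5 is in dispute.

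**2. Can a 20 mg dose be made?** Tablets per dose = dose / strength.

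- From 30 mg tablets: 20/30 = 2/3 of a tablet. Whole tablets give 0, 30 or 60 mg per dose. Half tablets add 15 and 45 mg. None is 20 mg.
- From 10 mg tablets: 20/10 = 2 tablets.

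**3. The four pairings of supply statement and dose rule.**

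| Supply after Day 5 | Dose rule | Can each dose be delivered? |
|---|---|---|
| 10 mg (synopsis, 5.2.1) | No modification (5.4.1) | Yes; no 20 mg dose needed |
| 10 mg (synopsis, 5.2.1) | Reduction to 20 mg BID (5.4.2) | Yes; 2 tablets per dose |
| 30 mg (5.2.2) | No modification (5.4.1) | Yes; no 20 mg dose needed |
| 30 mg (5.2.2) | Reduction to 20 mg BID (5.4.2) | No, unless another strength is dispensed |

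No section describes supplying a 20 mg tablet, returning to 10 mg tablets, or exchanging bottles after Day 6.

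**4. Expected tablets per day for the compliance count (section 5.3).**

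- 30 mg BID: 60/30 = 2 tablets of 30 mg, or 60/10 = 6 tablets of 10 mg.
- 20 mg BID: 40/10 = 4 tablets of 10 mg; no whole-tablet count exists for 30 mg tablets (40/30 = 1.33).

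Suppose a subject on 10 mg tablets is reduced to 20 mg BID and takes every dose. Against an expected count left at the full dose, compliance reads 4/6 = 67%, below 80%. Against an updated count it reads 4/4 = 100%. Section 5.3 refers to the expected regimen but does not say how it is reset after a reduction. Under section 6.7, a second shortfall after reinforcement leads to consideration for withdrawal. Section 9.1 defines the per-protocol population by sufficient compliance, without a threshold. One subject is 1/10 = 10% of the planned sample.

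**The case against.** The strongest reply is that a reader who sets section 5.2.2 beside section 5.4.2 might infer that the reduced dose simply cannot be taken from the study product. The documents do not support that. The synopsis and section 5.2.1 describe 10 mg tablets, from which 20 mg is two tablets. Section 5.2.2 does not say that 10 mg tablets are withdrawn or may not be dispensed again. Table 1 provides regular visits at which bottles change hands, and section 6.6 allows unscheduled ones. Nor is the reduction plainly compulsory: section 5.4.1 denies any modification, and section 5.4.2 leaves adjustments to the investigator immediately before giving the rule. The delivery problem also disappears if either of the other two contradictions is settled one way. All of this stands.

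Two further inferences should be resisted. The whole period from Day 6 to the end of treatment is the window in which a reduction could be ordered, not exposure known to be affected. And although sections 1.6.3 and 1.8 call most events mild or moderate, they pool the two grades and give only a reporting threshold of more than 5% for the commonest events. They supply no rate for the mild events that trigger section 5.4.2, so no count of affected subjects follows.

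The reply does not remove the conflict. If 5.2.2 is right, the synopsis and 5.2.1 are incomplete, and any reduction needs a supply that is not described. If they are right, the Day 6 sentence in 5.2.2 is wrong. Likewise 5.4.1 and the reduction sentence in 5.4.2 cannot both stand as written.

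**Conclusion.** The point holds as an internal contradiction in two parts: tablet strength after Day 5, and whether the dose may be reduced. One of the four pairings leaves 20 mg BID undeliverable from whole or half tablets; the other three do not. In every pairing that permits reduction, the tablet-count rule needs an expected count that the protocol does not state. The possible misreading there is 67% against an 80% threshold for a fully adherent subject, on the assumption that 10 mg tablets are used and the expected count is not reset.

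The number of subjects affected cannot be estimated from the documents. The conclusion assumes that tablets are taken whole or halved. It takes no position on which supply or which dose rule is correct. The correction should be made because it bears on dosing safety and on the compliance measure, and it costs little.

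**What to change.** Reconcile the synopsis drug paragraph and sections 5.2.1, 5.2.2, 5.4.1 and 5.4.2 so that every dose the protocol allows can be delivered from the strengths it supplies. The sponsor and investigator decide which supply and which dose rule apply. If more than one strength may be used after Day 6, say how and at which visit bottles are exchanged.

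In section 5.3, state the expected tablets per day for each allowed regimen and strength, and how the count is reset if the regimen changes between visits. In section 10.2, add tablet strength and the date of any change to the accountability record. That section already asks for dates, quantities and available batch numbers but does not mention strength, and it refers to tube counts for a tablet product.

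The cost is wording in a few sections and, if the sponsor so chooses, keeping stock of the 10 mg tablets already used for titration. Neither the sample size nor the primary analysis changes.

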5.2.3. Storage

Apremilast tablets should be stored between 15°C and 30°C (59°F and 86°F).

5.3. Treatment Compliance

Compliance will be assessed by reviewing the number of tablets remaining at each visit. Subjects will also be questioned regarding study drug use, missing doses, and use of any additional topical or systemic prescriptions of other products or over the counter products. Subjects who are noncompliant with study drug (defined as < 80% compliant based on expected regimen and number of tablets remaining) will have their instructions reinforced by the investigator or a qualified designee. Subjects will be considered compliant with the treatment regimen if they take at least 80% of the expected medications in the treatment phase of the study. Subjects who are noncompliant on more than 1 occasion will be reinstructed by the investigator or a qualified designee, and the sponsor should be consulted by the investigator for instruction on the proper handling of the subject.

5.4. Treatment Interruptions and Adjustments

5.4.1. Dose Modifications

No dose modifications are present in this trial.

5.4.2. Criteria and Procedures for Dose Interruptions and Adjustments of Study Drug

In some circumstances, it may be necessary to temporarily interrupt treatment as a result of AEs or laboratory abnormalities that may have an unclear relationship to study drug. Decisions on dose interruptions or adjustments will be made by the investigator. Should the subject experience a mild AE or laboratory abnormality, the dose will be reduced to 20 mg BID.

Individual subjects may have administration interrupted at the discretion of the investigator for AEs or laboratory abnormalities until these have resolved. Subjects will have administration interrupted in the following situations.

- The subject develops a Grade 2 increase in ALT ($> 3 \times \text{ULN}$) or AST ($> 3 \times \text{ULN}$), or a Grade 2 decrease in ANC ($< 1.5 \times 10^9/\text{L}$) or platelets ($< 75 \times 10^9/\text{L}$), or a Grade 3 decrease in absolute lymphocyte count ($< 0.5 \times 10^9/\text{L}$). Laboratory abnormalities should be confirmed with repeat testing within 48 hours whenever possible and STAT delivery of the laboratory results requested.
- The subject develops a Grade 3 or higher laboratory abnormality, with the exceptions of lipase (in which case a Grade 4, $> 5 \times \text{ULN}$, results in discontinuation of study medication) or any asymptomatic triglyceride, cholesterol, or amylase elevations. Laboratory abnormalities should be

confirmed with repeat testing within a medically indicated timeframe, based upon the investigator's judgment and in collaboration with the sponsor's medical monitor, and STAT delivery of the laboratory results requested.

- The subject had a severe drug-related AE as determined by the investigator.

5.4.3. **Criteria for Permanent Discontinuation of Study Drug**

Subjects who have administration interrupted based on the above criteria will be followed until the parameters return to the normal range or to baseline values. Laboratory evaluations can be repeated as frequently as daily. A subject who has had their dose interrupted based on these criteria may resume administration with study drug at a later time if the subject no longer meets the criteria for interrupting the dose with the sponsor's approval in consultation with the investigator. Subjects who meet withdrawal criteria (see Section 5.5) during study drug interruption will be withdrawn from the study and may not resume administration.

5.5. **Withdrawal of Subjects From Study Treatment**

5.5.1. **Withdrawal Criteria**

Subjects **must** be withdrawn from study treatment for the following reasons:

- The subject becomes pregnant.
- Consent is withdrawn.
- Further participation would be injurious to the subject's health or well-being, in the Investigator's medical judgment.
- The study is terminated by the local health authority, IRB, or IEC.
- The subject has a dose interruption for >2 weeks

A subject **may** be discontinued from study treatment as follows:

- If, during the course of the study, a subject is found not to have met eligibility criteria, the investigator will determine whether the subject should be withdrawn from the study.
- If a subject is noncompliant with study procedures or study drug administration in the Investigator's opinion.

5.5.2. **Withdrawal Procedures**

In the event that the decision is made to permanently discontinue the study drug, the subject will be withdrawn from the study and the end-of-treatment visit should be conducted. Reasonable efforts should be made to have the subject return for a follow-up visit. The last date of the last dose of study drug and the reason for subject withdrawal will be recorded in the source document.

If a subject is withdrawn from the study

- The reason(s) for withdrawal must be documented in the subject's medical record and in the source document.
- The EOT visit should be performed.
- Subjects must be followed for safety until the time of the follow-up visit or until study drug-related toxicities resolve, return to baseline, or are deemed irreversible, whichever is longest.

If the subject discontinues study treatment and actively withdraws consent for collection of follow-up data (safety follow-up or disease assessment), then no additional data collection should occur; however, subjects will have the option of withdrawing consent for study treatment but continuing in the follow-up period of the study for safety/efficacy assessments.

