7.4.5. Laboratory Assessments

Clinical laboratory tests will be performed using a central laboratory. A detailed description of the procedures for sampling, handling, storage, and shipment of the

central laboratory samples and all material such as test tubes and labels is provided in the central Laboratory Manual. If unscheduled local laboratory tests are performed and those results lead to a dose modification, delay, or dose interruption, or any additional non-Protocol-required test is performed because of an AE, those results and the normal reference ranges for those analytes must be documented in the source document. Otherwise, unscheduled local laboratory test results need not be entered in the source document.

Tests required at each visit are shown in Table 1. Additional analytes may be requested based on emerging data, if indicated for safety of study subjects. In addition, some subjects may receive additional assessments as medically indicated; results of nonrequired tests may also be entered in the source document.

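### Sections 5.4.1 and 5.4.2 give opposite dosing rules for a mild adverse event, and the 5.4.2 reduction, taken literally, is too broad and would raise the dose on titration Days 1 to 3

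*Combined protocol and SAP*

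**What the plan says.** Section 5.4.1 consists of one sentence: "No dose modifications are present in this trial". Section 5.4.2 then says "Decisions on dose interruptions or adjustments will be made by the investigator" and continues "Should the subject experience a mild AE or laboratory abnormality, the dose will be reduced to 20 mg BID". Further down the same section, one of the triggers for interruption reads "The subject had a severe drug-related AE as determined by the investigator". Section 5.4.3 deals with restarting: "A subject who has had their dose interrupted based on these criteria may resume administration with study drug at a later time". It covers return after an interruption and does not mention return to full dose after a reduction.

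Other places bear on the conflict:

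- Section 4.1 states "All subjects will receive apremilast 30 mg by mouth BID for 16 weeks", and the primary objective in 2.1.1 names 30 mg BID.
- Section 7.4.5 provides for unscheduled local tests where "those results lead to a dose modification, delay, or dose interruption". Section 8.1.1 likewise counts a laboratory abnormality that requires a change of dose as an adverse event.
- The Synopsis and 5.2.1 describe 10 mg tablets. Section 5.2.2 supplies 10 mg tablets for titration and 30 mg tablets from Day 6.
- Sections 5.3 and 6.7 set an 80% compliance limit. Section 5.3 refers to the expected regimen and the tablets remaining; 6.7 refers only to the number of tablets.

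**The concern.** A mild adverse event is foreseeable. Sections 1.6.3 and 1.8 list diarrhea, nausea, headache, upper respiratory infection and nasopharyngitis as each reported in more than 5% of subjects. They describe most events as mild or moderate, and say most diarrhea, nausea and headache begins in the first 2 weeks. For such an event one section forbids a dose change and the next requires one, so two subjects with the same event could end up on different doses.

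If 5.4.2 is the intended rule, three things are wrong with it as written. A mild cold with no suspected link to the drug would trigger a cut. An event in the first days of titration would trigger an increase. The tablets named in 5.2.2 for maintenance cannot deliver the reduced dose. What is at stake is the dose subjects actually take in a trial of 10 with no replacement (4.3), and how the result is described when the objective names 30 mg BID.

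**Working it through.** The plan states no figure on this point, so the check is a comparison of text plus simple dose arithmetic.

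**Step 1: can both rules be followed?** Going from 30 to 20 mg BID is a dose modification on any ordinary reading. Section 5.4.1 has no qualifier such as *planned* or *other than below*, and the reduction in 5.4.2 is itself written in advance as something that will happen. Both cannot hold.

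**Step 2: does other text settle it?**

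| Points to 5.4.2 | Points to 5.4.1 |
|---|---|
| Headings of 5.4 and 5.4.2 both mention adjustments | 5.4.1 itself, unqualified |
| 5.4.2 gives adjustment decisions to the investigator | 4.1: 30 mg BID for all, 16 weeks |
| 7.4.5 and 8.1.1 presuppose dose modification | 2.1.1: objective names 30 mg BID |

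The weight lies with 5.4.2. Section 4.1 also leaves out the titration in 5.2.1, so it describes the planned regimen and does not bar a reduction. Still, no sentence ranks the two rules.

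**Step 3: the relatedness condition.** The severe-event trigger in 5.4.2 requires a drug-related event. The reduction sentence has no such condition. The remark at the start of 5.4.2 about an unclear relationship to study drug concerns temporary interruption.

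**Step 4: the reduction during titration.** Daily doses are from 5.2.1; the reduced dose is 2 × 20 = 40 mg/day.

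| Day | Scheduled (mg/day) | Literal effect of moving to 40 mg/day |
|---|---|---|
| 1 | 10 | +30 |
| 2 | 20 | +20 |
| 3 | 30 | +10 |
| 4 | 40 | 0 |
| 5 | 50 | −10 |
| 6 onward | 60 | −20 |

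The rule raises the dose on Days 1 to 3, leaves it unchanged on Day 4, and lowers it only from Day 5.

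**Step 5: size of the reduction in maintenance.** 40/60 = 66.7% of the planned daily dose.

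**Step 6: supply.** 20/30 = two-thirds of a 30 mg tablet, so whole 30 mg tablets cannot give 20 mg. Two 10 mg tablets can.

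**Step 7: compliance, if the expected regimen were left at 30 mg BID.** Each reduced maintenance day loses 20 mg.

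- Baseline to Week 2: planned (10 + 20 + 30 + 40 + 50) + 9 × 60 = 150 + 540 = 690 mg. Six reduced days: 570/690 = 82.6%. Seven: 550/690 = 79.7%, below 80%.
- Weeks 2 to 4: planned 14 × 60 = 840 mg. Eight reduced days: 680/840 = 81.0%. Nine: 660/840 = 78.6%, below 80%.
- If the expected regimen is the reduced one, a subject who takes it as told is at 100%.

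These are ratios of milligrams, whereas 5.3 and 6.7 count tablets. The two agree only if 10 mg tablets are used throughout, and in that case the supply problem of Step 6 does not arise. With 30 mg tablets in maintenance, a reduced subject would take four 10 mg tablets a day against two 30 mg tablets expected, and a raw count would not give 66.7%.

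**The case against.** The best reply is that context already resolves the conflict. A specific instruction normally overrides a general sentence, the investigator decides on adjustments, and several sections assume that doses can change. On that view 5.4.1 is a drafting remnant. Much of this stands: 5.4.2 is the more likely intent. It does not dispose of the point, because the protocol never says so, and because choosing 5.4.2 leaves the defects of Steps 3, 4 and 6 in place.

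On supply, it can fairly be said that 10 mg tablets are already on hand for titration, that drug is handled at every treatment visit, and that 6.6 allows unscheduled visits. The problem is therefore small in practice, but the three sections on tablet strength still disagree.

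A reader might go further and infer that subjects correctly taking 20 mg BID will fail the 80% check and be withdrawn from a trial of 10. The documents do not support that. The expected regimen in 5.3 most naturally means the dose the investigator has ordered. Section 6.7 says only that a subject who falls short again is considered for withdrawal, and 5.5.1 makes withdrawal for noncompliance optional. The supply and compliance problems also cannot simply be added together, for the reason given at the end of Step 7.

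**Conclusion.** The dosing text is wrong as written and should be corrected. Two adjacent current rules conflict. The one that context favours has no relatedness condition, raises the dose on three of the five titration days, and does not fit the tablet strength in 5.2.2.

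The size per reduced subject is a one-third cut in maintenance dose. How many subjects would be reduced cannot be derived: the documents give no mild-event rate, so the range is 0 to 10. The laboratory trigger should seldom matter on treatment, since scheduled safety laboratories fall only at screening and Week 16.

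The compliance question is a minor clarification. A reader might also infer that the primary analysis is compromised; it is not. The paired t-test in 9.4.1.2 does not depend on the dose taken, no analysis in 9.4 uses the per-protocol set, and the interruption and withdrawal rules stand. What changes is the description: with reductions allowed, the result is for a 30 mg BID regimen with reduction permitted.

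**What to change.** 1. Section 5.4.1: state that there are no dose modifications other than those in 5.4.2.
2. Section 5.4.2: limit the reduction to 20 mg BID to a mild adverse event or laboratory abnormality suspected to be drug-related, during maintenance dosing (Day 6 onward).
3. Synopsis, 5.2.1 and 5.2.2: give the same maintenance tablet strength, and keep 10 mg tablets available after Day 6.
4. Sections 5.3 and 6.7: add that a reduced subject is judged against the reduced regimen from the date of reduction.
5. Section 9: add one sentence to report the number and timing of reductions, and describe the result as 30 mg BID with reduction allowed.

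Three clinical choices belong to the investigator and sponsor: whether the reduction is mandatory or discretionary, whether and when a subject returns to 30 mg BID, and whether the trigger should extend beyond mild events. A discretionary rule would still allow subjects with the same event to be dosed differently, so if it is chosen the protocol should say so openly.

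The cost is a short text amendment and a small reserve of 10 mg tablets. No additional subjects, visits or tests are needed.
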